4.2 Active surveillance and screening

The detailed screening methods to conduct active surveillance will be determined by the site and described in full in a Surveillance Manual which will be created and managed by the Investigator and reviewed by Pfizer collaborators. The feasibility studies conducted prior to the surveillance study implementation will inform the detail of surveillance activities and screening processes at both locations.

In essence, any adult inpatients ≥ 18 years old presenting to one of the participating hospitals displaying the specified symptoms of LRTD or with a clinical diagnosis consistent with LRTD will be included in the screening activities, including those with exacerbations of COPD and CHF accompanied

by respiratory symptoms. Screening for potential Avon CAP study participants will be undertaken by a member of the clinical team at each hospital site, usually a nurse, allied health professional (e.g. physiotherapist) or doctor. This should be performed at least once a daily during the working week (Mon-Fri), with the first screening round performed at the start of the day. Screening will involve reviewing the medical admission take list (primarily the 'presenting complaint/details' section) to screen patients for entry to the surveillance part of the study. The medical admission list is a real-time electronic based list (internet or other IT system) which can be searched using various parameters including admission time, enabling accurate checking of patient admissions (especially those occurring overnight and at weekends). The medical admission take list also records details of the presenting complaint and/or presumed diagnosis of each patient admitted to the hospital.

Patients admitted through the medical admission take will be excluded if they have a presenting complaint or diagnosis that is not compatible with the study inclusion/exclusion criteria. For example, patients without lower respiratory pathology such as acute pancreatitis, myocardial infarction (NSTEMI or STEMI), stroke or cellulitis would be excluded from entering the surveillance log.

Following consent, participants with LRTD events meeting the screening definition will undergo enhanced diagnostic tests and have their clinical data pseudonymised and entered into the eCRF. All potential participants will be approached regardless of time of admission if they are present during established recruitment periods.

4.3 Pseudonymisation

Each patient with an admission that may meet eligibility will be assigned a surveillance number within the database. This will be assigned by the research team following the screening of the medical admission list and will be used to pseudonymise patients. Throughout the study and on its completion, the database will be cleaned using the NHS number to identify individuals who have more than one qualifying admission, both within one NHS Trust and across participating study sites. These individuals will be identified in the pseudonymised database using the surveillance number of their first study eligible admission. The NHS number will subsequently be deleted following processing at the end of the study. This will provide a method of ensuring that there is an accurate calculation of disease incidence within a defined geographical area with multiple NHS hospitals providing acute care, whilst maintaining a pseudonymised database. A data flow diagram is included in Section 11.4.

4.4 Patient selection

4.4.1 Screening inclusion criteria

Patients must meet all the following inclusion criteria to be eligible for enrolment:

1. Aged ≥ 18 years of age
2. Patients with illness with following 2 characteristics:
 - a. Acute illness (i.e., present for 28 days or less); **AND**
 - b. Evidence of acute LRTD:
 - i. Patients with current or suspected COVID-19 or previous proven COVID-19 within last 28 days **OR**
 - ii. Clinical or radiologic diagnosis of pneumonia or an acute LRTI **OR**
 - iii. New onset or worsening of ≥ 2 of following 8 LRTD symptoms or clinical findings:
 1. fever ($>38.0^{\circ}\text{C}$) or hypothermia ($<35.5^{\circ}\text{C}$) before or within 24 hours of enrolment;
 2. pleuritic chest pain;
 3. cough (including nocturnal only);
 4. sputum production or purulence;
 5. dyspnea (shortness of breath) including orthopnea or on exertion only;
 6. tachypnea (respiratory rate $\geq 20/\text{min}$) documented by healthcare professional;
 7. abnormal auscultatory findings suggestive of LRTD (e.g., crackles/rales or evidence of pulmonary consolidation including dullness on percussion, bronchial breath sounds, wheezing, or egophony);
 8. radiologic finding that is consistent with LRTD, including pneumonia, and/or acute congestive heart failure (e.g., pleural effusion, increased pulmonary density due to infection, the presence of alveolar infiltrates [multilobar, lobar or segmental] containing air bronchograms, or interstitial oedema).

4.4.2 Screening exclusion criteria

Patients meeting any of the following criteria will not be included in the study:

1. Any patient who develops signs and symptoms of LRTD after being hospitalized for ≥ 48 hours (either at current hospital, another transferring hospital, or a combination of these), unless admitted with current, previous proven, or suspected COVID-19 infection.
2. Previously enrolled participants readmitted ≤ 7 days after discharge for their study qualifying admission, unless admitted with current, previous proven, or suspected COVID-19 infection
3. At the time of enrolment, an LRTD-related diagnosis has been excluded or another diagnosis confirmed (for example, patient was found to have fever and tachypnoea due to an intraabdominal process such as cholecystitis)

4.4.3 Study inclusion/exclusion criteria

To participate in the enhanced diagnostic testing, individuals must meet all of the following:

1. Meet all screening inclusion criteria in section 5.2.2
2. Meet none of screening exclusion in section 5.2.3
3. Informed consent document signed and dated by patient (if written consent) or otherwise documented (as detailed below), or the requirements for patients unable to provide consent have been fulfilled (as detailed below)

4.4.4 UAD and respiratory pathogen control group

4.4.4.1 Control group inclusion criteria

Individuals must meet all of the following inclusion criteria:

1. Age 18 years and older.
2. Informed consent document signed and dated by patient
3. Individuals who are willing and able to provide urine and respiratory swab

4.4.4.2 Control group exclusion criteria

Individuals presenting with any of the following will not be included in the control group:

1. Individuals who are investigational site staff members or relatives of those site staff member or participants who are Pfizer employees directly involved in the conduct of the trial.

2. Individuals with suspicion of pneumonia or other respiratory infectious diseases or documented, concomitant infectious disease.
3. Individuals residing in any long-term care facilities (for example, nursing homes or respite care facilities).
4. Individuals with known bronchial obstruction or a history of post-obstructive pneumonia. (Chronic obstructive pulmonary disease (COPD) is permissible, provided there has not been an exacerbation within the 3 months prior to enrolment.)
5. Individuals with primary lung cancer or another malignancy metastatic to the lungs.
6. Individuals with fever (measured temperature of $\geq 38.0^{\circ}\text{C}$ measured by a healthcare provider).
7. Individuals with significant immunosuppressive disease such as leukaemia.
8. Individuals with either pneumococcal conjugate vaccine (PCV) and/or pneumococcal polysaccharide vaccine (PPV) administration within the past 30 days

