4. Patients currently admitted at participating hospitals on non-medical wards with no current acute respiratory or cardiovascular conditions.

Control participants will provide urine for UAD and BinaxNOW testing and an upper respiratory swab sample for RSV/respiratory pathogen testing. UAD testing will help inform cut points for UAD positivity in this population.

COVID-19 VE assessment is described in Appendix 1.

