9.2.3 Cardiovascular events following pneumonia

The rates of cardiovascular events at 30 days following pneumonia will be compared to rates among controls without acute LRTD in the 2 months prior to their enrollment. In addition, a group of comparable persons based on age, Charlson co-morbidity index and underlying disease will be assembled through analysis of anonymized health data to assess the rate of these outcomes in this population with pneumonia. Full details will be provided in the SAP.

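### The control exclusions have no look-back for pneumonia or LRTI (post-obstructive pneumonia apart), so recently infected people can enter the UAD control set and the cardiovascular comparator; the likely effect is small and the remedy cheap

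*Protocol*

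**What the plan says.** Section 4.1 plans about 400 controls without acute LRTD, comparable to the enhanced-testing participants by age group and season. They come from outpatient clinics other than respiratory and cardiology, or from "non-medical wards with no current acute respiratory or cardiovascular conditions".

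Section 4.4.4.2 lists the exclusions. Four matter here:

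- Item 2: "Individuals with suspicion of pneumonia or other respiratory infectious diseases or documented, concomitant infectious disease".
- Item 4: "Individuals with known bronchial obstruction or a history of post-obstructive pneumonia". COPD "is permissible, provided there has not been an exacerbation within the 3 months prior to enrolment".
- Item 6: a measured fever.
- Item 8: pneumococcal conjugate or "pneumococcal polysaccharide vaccine (PPV) administration within the past 30 days".

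The controls have two uses relevant to this point. For the urinary antigen assay, section 4.1 says "UAD testing will help inform cut points for UAD positivity in this population", while section 6.3.4 describes the samples as supporting cut-offs that are already established. For cardiovascular events, section 9.2.3 says that 30-day rates after pneumonia "will be compared to rates among controls without acute LRTD in the 2 months prior to their enrollment". Table 3 and its footnote ask for control cardiovascular events over the past 2 months.

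**The concern.** Item 2 and item 6 describe how the person is on the day. Neither they nor the source definitions in 4.1 ask about the preceding weeks. Yet the list treats a COPD exacerbation up to 3 months old, and pneumococcal vaccine up to 30 days old, as reasons to exclude. A recent pneumococcal pneumonia is both a recent respiratory illness and a recent exposure to pneumococcal antigen, and it has no window.

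Two uses are exposed:

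- **Cardiovascular comparator.** A control who had pneumonia during the 2-month window contributes post-pneumonia time, which is the exposure under study, to the unexposed rate. If pneumonia raises the cardiovascular rate, the contrast shrinks toward the null.
- **UAD assessment.** Controls should be free of pneumococcal disease. Residual antigen in a recently infected control would either push a cut-off upward or make an established one look less specific than it is.

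**Working it through.** **1. Does any rule close the gap?** Take a person who had pneumonia two weeks ago, has recovered, is afebrile, and attends a surgical clinic.

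| Rule | Catches this person? |
|---|---|
| 4.1 source: outpatient, not respiratory or cardiology | No |
| 4.1 source: inpatient, no current acute condition | No, refers to the present |
| 4.4.4.1 inclusion criteria (age, consent, able to give samples) | No |
| 4.4.4.2 item 2 (suspected or concomitant infection) | No, refers to the present |
| 4.4.4.2 item 4 (post-obstructive pneumonia; COPD exacerbation) | Only that subtype, or only with COPD |
| 4.4.4.2 item 6 (measured fever) | No |
| 4.4.4.2 item 8 (pneumococcal vaccine) | No, vaccine only |

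The wording of 9.2.3 could be read as requiring no LRTD over the 2 months. Table 3 and its footnote show that the 2 months is the period for collecting cardiovascular events, and 4.4.4.2 contains no such LRTD-free rule.

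**2. How many controls might be affected?** Inputs from the protocol: hospitalised LRTD 3.65 per 100 person-years (9.1); pneumonia 0.5 to 1% of adults per year (1.1); LRTI 148 per 1000 person-years at 65 and over (1.1); 400 controls (4.1).

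The figure in 9.1 reproduces: 23,000 / 630,000 = 3.65 per 100, with 95% CI 3.65 ± 1.96 × 100 × √(0.0365 × 0.9635 / 630,000) = 3.60 to 3.70.

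Expected number = 400 × (1 − exp(−rate × days / 365.25)):

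| Event | Within 60 days | Within 91 days |
|---|---|---|
| Pneumonia, 0.5% per year | 0.3 (0.08%) | 0.5 |
| Pneumonia, 1% per year | 0.7 (0.16%) | 1.0 |
| Hospitalised LRTD, 3.65/100 py | 2.4 (0.60%) | 3.6 |
| LRTI, if every control were 65 or over | 9.6 (2.40%) | 14.5 |

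**3. What would that do to the cardiovascular ratio?** With a share q of controls affected, a fraction f of their window spent at raised risk, and a true rate ratio RR, the comparator is inflated by 1 + q·f·(RR − 1). The protocol gives no RR, so RR = 5 is an assumption for illustration; a smaller RR gives a smaller proportional bias. f = 1 is an upper bound. If onset is uniform over 60 days and the raised rate lasts 30 days, the mean time at risk is (30 × 15 + 30 × 30) / 60 = 22.5 days, so f = 22.5 / 60 = 0.375.

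| q | Ratio read at f = 1 | Ratio read at f = 0.375 |
|---|---|---|
| 0.16% (pneumonia, 1% per year) | 5 / 1.0064 = 4.97 | 5 / 1.0024 = 4.99 |
| 0.60% (hospitalised LRTD) | 5 / 1.024 = 4.88 | 5 / 1.009 = 4.96 |
| 2.40% (LRTI, all 65 or over) | 5 / 1.096 = 4.56 | 5 / 1.036 = 4.83 |

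The last two rows generously apply the pneumonia ratio to LRTD and LRTI of every kind.

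**4. UAD.** The protocol gives neither how long antigen persists in urine nor how a cut-off would be set from controls. Only the direction can be stated.

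**The case against.** The strongest reply is that little depends on this.

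- **The UAD cut-offs are described as established (6.3.4) and UAD 1 as validated.** This stands. A reader might infer that contaminated controls would raise the cut-offs, lower UAD sensitivity and so depress pneumococcal and vaccine-type incidence. The protocol does not support that chain: nothing in it derives a cut-off from these 400 people, and 4.1 says only that they help inform it.
- **The prevalence is low.** This stands for general-population rates. A reader might take a figure such as 3% of controls with pneumonia in the previous 2 months, which at a rate ratio of 5 and f = 1 inflates the comparator by 12%. That is about 18 to 36 times the pneumonia rates in section 1.1, and it counts the whole window as post-pneumonia time. However, controls are hospital attenders of similar age group and season to the cases, so all-adult annual averages may understate their risk.
- **The cardiovascular objective is exploratory (3.3.1), 9.2.3 adds a second comparator from anonymised health data, and full details are left to the SAP.** This limits the consequence. Eligibility, however, is fixed in the protocol, and a SAP can only remove such controls after enrolment.
- **The COPD clause qualifies the bronchial-obstruction exclusion and was not offered as a general infection window.** This is fair: item 2 does not contradict a stated standard. The different look-backs are an unevenness in the list, and the case for change rests on how the controls are used.

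**Conclusion.** The gap is real: apart from post-obstructive pneumonia, 4.4.4.2 has no look-back for pneumonia or LRTI, and no other control criterion supplies one. The cardiovascular contrast would be biased toward the null if pneumonia raises the event rate.

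The size is probably small. On the protocol's rates, fewer than one control would have had recent pneumonia and between two and three a recent hospitalised LRTD; the count approaches ten only for any LRTI in a group made up entirely of people aged 65 or over. An assumed ratio of 5 would read 4.97 to 4.99 at the upper pneumonia rate, and no lower than 4.56 in the most extreme case tabulated. These figures assume that general-population rates apply to hospital-based controls, who may run higher; the COPD and long-term-care exclusions act the other way. The UAD effect has a direction but no computable size. No primary or secondary estimate is shown to move. The point is a low-cost tightening of a control definition and does not threaten the study's main results.

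**What to change.** 1. Add to 4.4.4.2 an exclusion for pneumonia or LRTI, including a study-qualifying LRTD admission, within a stated period before enrolment. The period should cover at least the 2-month event window; 3 months would match the COPD look-back. Check it at the patient interview and medical record review that Table 3 already schedules.
2. For controls already enrolled, apply the same rule as an analysis exclusion in the UAD cut-off assessment and in the 9.2.3 comparison.
3. Reword 9.2.3 so that it is clear that the 2 months is the period over which cardiovascular events are counted, and that controls must have been free of LRTD throughout it.

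The cost is an extra question at a visit that already takes place, and a few controls replaced or dropped. With a 3-month window, the rates above suggest about 4 of 400 on hospitalised LRTD, and up to about 15 for any LRTI if all controls were 65 or over. No link to the pseudonymised surveillance database is needed.

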4.4.5 Patient consent and enrolment

Avon CAP is a disease surveillance study for acute LRTD illness events occurring in hospitalised patients recording clinical data and the results of investigations performed by clinical teams as routine standard-of-care. Therefore, specified individual patient consent is not required to collect data on acute LRTD events for screening.

Patients with LRTD illness event identified through screening will be offered the opportunity to participate in enhanced diagnostic testing portion of this study. This enhanced diagnostic testing requires informed consent to participate and involves collection of urine, blood and upper respiratory swabs, as well as extra interview data and access to data held in the surveillance database. Participants will have an opportunity to review information about what would be involved in full in the patient information leaflet and informed consent form.

This study anticipates that some patients who meet eligibility criteria may not be able to provide consent. For example, patients requiring ventilation on intensive care, or those with delirium or cognitive impairment and/or dementia may lack capacity. In this event, the research team will discuss the patient's capacity with the relevant clinical team and determine the opinion of the clinical team concerning the patient's capacity and willingness to participate. The research team will attempt to contact a family member, friend or unpaid carer of the patient (i.e. patient representative), in order to discuss the study and determine the patient's willingness to participate. The patient will not be enrolled in the study if the research team, clinical team or patient representative do not feel that this patient would be willing to participate if they had capacity, or that participating would adversely affect

their clinical treatment. We will conduct this aspect of the study in accordance with the Mental Capacity Act.

Consent or a consultee declaration can be taken face-to-face with individuals who are currently in the hospital or on hospital site. This study anticipates instances when face-to-face discussions and written documentation may not be possible. Such examples include infection control measures restricting hospital visiting, participants who have been discharged before the research team could approach and participants with difficulty in completing the consent form (e.g. osteoarthritis). In cases where face-to-face and/or written consent is not possible, alternate methods of consent and its documentation may be used: including (but not limited to) electronic, telephone or other verbal consent (e.g. teleconference). If a consent or declaration form is not completed and signed by the participant or consultee, then research staff will ensure that there is a witness to countersign the appropriate consent or declaration form.

Avon CAP is an observational surveillance study, and patients can, therefore, be enrolled in other studies or clinical trials. Furthermore, the study anticipates that one individual may have multiple study eligible hospitalizations throughout the duration of the study, as they may be admitted with multiple chest infections or respiratory exacerbations. If the research team become aware that a potentially eligible participant has previously consented to enrol in the study during a previous hospital admission, they will seek confirmation that the participant is willing to consent to ongoing participation during the relevant study eligible admission. This may be in the form of repeated consent to enrol or via a declaration that the previous consent is still valid as there has been no change in the study processes or protocols, and that the participant is still willing to consent to enrolment.

5 Justification for accessing data without consent

The Avon CAP surveillance study will undertake comprehensive surveillance on all adults hospitalised with an eligible condition (i.e. acute LRTD) without consent from all participants.

Avon CAP will undertake systematic and comprehensive surveillance of all adults hospitalized with acute lower respiratory tract disease within a well-defined geographical area. As the demographic and population of Bristol is well described, ascertaining the true burden of acute respiratory infection and describing disease in the context of COVID-19 will allow this study to calculate accurate estimates of incidence. In order to be able to determine the morbidity and mortality associated with acute lower respiratory tract disease, it is necessary that the data collected cover the entire population, as missing any cases within the study area would result in an inaccurate calculation of disease burden. Furthermore, by capturing and detailing precise clinical data, this study will be able to stratify disease by patient factors such as age, gender and ethnicity, as well as by risk factors, including smoking status and pre-existing co-morbid disease including chronic respiratory and cardiovascular conditions. Through this surveillance mechanism all acute respiratory infection in hospitalized adults will also be described by causative pathogen and radiological diagnosis, in addition to capturing patient outcome. The study has three important features:

1. The data will be comprehensive and complete over a defined time period for a defined population area and therefore not subject to the potentially biased ascertainment which weakens other large studies
2. The demographic of the study area is broad in terms of deprivation, minority groups, urban and rural distribution and is in many ways highly representative of the population of England, permitting results to be of value for nationwide planning.
3. The study has substantial confirmed funding which will underpin its viability and successful conduct and is fully embedded within the clinical services of the contributing hospitals, while the anonymised data handling and analysis will be undertaken within the University domain thus not competing for scarce research resources at a time of critical need within the NIHR and NHS research infrastructures.

This comprehensive surveillance platform will enable us to truly understand and describe adult respiratory infection in adults in the context of COVID-19. Should any vaccine providing protection against respiratory pathogens be introduced during Avon CAP, the design of this study enables it to act as a vaccine impact ecological study. The research team will seek to enrol as many participants as possible in the embedded study undertaking enhanced diagnostic tests, with a target recruitment of 80% of eligible participants.

